### **4.4 Justification for Doses of RXC004 and Nivolumab**

Patients who enrol in Arm A RXC004 monotherapy will receive 2.0 mg RXC004 orally once a day in a fasted state. This dose was chosen using the predicted efficacious dose ranges from pre-clinical pharmacology models, preclinical and clinical target engagement assays, information from toxicology and toxicokinetic studies, and safety, efficacy and pharmacokinetics data from the Phase 1 study of RXC004 in patients with advanced solid tumours (NCT03447470).

Patients who receive combination therapy with RXC004 and nivolumab in Arm A or B will receive RXC004 1.5 mg orally once a day in combination with nivolumab 480 mg q4w. The RXC004 1.5 mg dose is supported by the available safety and PK data for this dose given in combination with nivolumab in the ongoing Phase 1 study RXC004/0001 (NCT03447470; see Sections 4.4.1.2 and 4.4.1.3). At a meeting held on 07 July 2022, the Phase 1 Safety Review Committee (SRC) determined that RXC004 1.5 mg in combination with nivolumab is a tolerated dose, based on safety and PK data (see Sections 4.4.1.2 and 4.4.1.3).

**Table 5 Summary of Treatment-Emergent Adverse Events Phase 1 study RXC004/0001, monotherapy Module 1)**

Number of patients with:	0.5 mg (N=4) N (%)	1.0 mg (N=3) N (%)	1.5 mg (N=7) N (%)	2.0 mg (N=6) N (%)	3.0 mg (N=4) N (%)	10.0 mg (N=1) N (%)	Overall (N=25) N (%)
Any TEAE	4 (100)	3 (100)	7 (100)	6 (100)	4 (100)	1 (100)	25 (100)
Any Treatment-Related TEAE	4 (100)	3 (100)	5 (71)	5 (83)	4 (100)	1 (100)	22 (88)
TEAE >= Grade 3	0 (0)	1 (33)	6 (86)	1 (17)	3 (75)	1 (100)	12 (48)
Treatment-Related TEAE >= Grade 3	0 (0)	0 (0)	2 (29)	1 (17)	1 (25)	1 (100)	5 (20)
Serious TEAE	0 (0)	1 (33)	5 (71)	117)	3 (75)	1 (100)	11 (44)
Serious Treatment-Related TEAE	0 (0)	0 (0)	1 (14)	0 (0)	2 (50)	1 (100)	4 (16)
TEAE Leading to Discontinuation of Study Treatment	1 (25)	0 (0)	2 (29)	0 (0)	2 (50)	1 (100)	6 (24)
Treatment-Related TEAE Leading to Discontinuation of Study Treatment	1 (25)	0 (0)	2 (29)	0 (0)	2 (50)	1 (100)	6 (24)
TEAE Leading to Dose Modification	0 (0)	1 (33)	3 (43)	2 (33)	2 (50)	1 (100)	9 (36)
TEAE Leading to Death	0 (0)	0 (0)	1 (14)	0 (0)	1 (25)	0 (0)	2 (8)

TEAE = treatment-emergent adverse event

The most common TEAEs and TRAEs (occurring in at least 20% patients) are summarised in Table 6 and Table 7. The most frequently occurring TEAEs were fatigue (64%), nausea (56%), decreased appetite (48%), vomiting (40%), dysgeusia (36%), diarrhoea (32%), aspartate aminotransferase increased (28%), anaemia (20%), and constipation (20%).

**Table 6** **Most common (occurring in at least 20% patients) treatment emergent AEs in Phase 1 study RXC004/0001 (monotherapy Module 1)**

Preferred Term	0.5 mg (N=4)	1.0 mg (N=3)	1.5 mg (N=7)	2.0 mg (N=6)	3.0 mg (N=4)	10.0 mg (N=1)	Overall (N=25)
Patients with Any TEAEs	4 (100)	3 (100)	7 (100)	6 (100)	4 (100)	1 (100)	25 (100)
Fatigue	2 (50)	2 (67)	6 (86)	3 (50)	2 (50)	1 (100)	16 (64)
Nausea	2 (50)	2 (67)	5 (71)	1 (17)	3 (75)	1 (100)	14 (56)
Decreased appetite	1 (25)	2 (67)	3 (43)	2 (33)	3 (75)	1 (100)	12 (48)
Vomiting	0 (0)	2 (67)	4 (57)	2 (33)	1 (25)	1 (100)	10 (40)
Dysgeusia	0 (0)	0 (0)	2 (29)	3 (50)	3 (75)	1 (100)	9 (36)
Diarrhoea	1 (25)	2 (67)	3 (43)	1 (17)	0 (0)	1 (100)	8 (32)
AST increased	1 (25)	0 (0)	3 (43)	1 (17)	1 (25)	1 (100)	7 (28)
Anaemia	1 (25)	2 (67)	2 (29)	0 (0)	0 (0)	0 (0)	5 (20)
Constipation	0 (0)	0 (0)	1 (14)	1 (17)	2 (50)	1 (100)	5 (20)

#### **4.4.1.2 RXC004 Clinical Safety Data (NCT03447470) – in Combination with Nivolumab Module 2)**

As of 01 July 2022, 13 patients have received RXC004 in combination with nivolumab 480 mg q4w at doses of RXC004 1 mg and 1.5 mg in Module 2 of the ongoing Phase 1 study RXC004/0001. Eight of these patients received treatment at the highest declared tolerated dose (RXC004 1.5 mg). Treatment-related AEs of CTCAE  $\geq$  Grade 2 reported in DLT-evaluable patients are summarised in Table 8.

Overall, the AE profile of the RXC004 1.5 mg dose in combination with nivolumab is similar to the RXC004 2 mg monotherapy dose. More patients who received the 1.5 mg dose had treatment related AEs of Grade 2 or higher (4/6) than patients who received the 1 mg dose (2/5). One patient who received 1.5 mg in combination had drug-induced liver injury (DILI), which was considered drug-related and a DLT.

The SRC determined at a meeting held on 07 July 2022, that both RXC004 1 mg and 1.5 mg QD in combination with nivolumab are tolerated doses. A decision was made not to further escalate the dose in the study, based on the safety and PK profiles of the 1.5 mg dose, as the combination of RXC004 2 mg with nivolumab was anticipated to lead to slightly higher exposure and potentially more AEs than the 2 mg monotherapy dose.

**Table 8 Treatment-related AEs Grade 2 or higher including DLTs, observed in DLT evaluable patients as of 01 July 2022, Phase 1 study RXC004/0001 (RXC004 + nivolumab Module 2)**

Dose	Number of patients dosed	Patients evaluable for DLT	Study treatment-related AEs, CTCAE $\geq$ Grade 2 in DLT-evaluable a patients
1.0 mg QD RXC004 + nivolumab 480 mg q4w	5	5	
Tolerated dose
 
Events <math>\geq</math> Grade 2 in DLT-evaluable patients (2/5 patients):
 
G2 back pain (1/5 patients) b
 
G2 nausea (1/5 patients) b
 
G2 fatigue (1/5 patients) c
 
G2 poor appetite (1/5 patients) c
 
G3 fatigue (1/5 patients) b

1.5 mg QD RXC004 + nivolumab 480 mg q4w	8	6 e	
Tolerated dose
 
Events <math>\geq</math> Grade 2 in DLT evaluable patients (4/6 patients):
 
G2 dysgeusia (2/6 patients) b
 
G2 diarrhoea (1/6 patients) b
 
G2 diarrhoea (1/6 patients) c
 
G2 reduced appetite (1/6 patients) b
 
G2 nausea (1/6 patients) b
 
G2 constipation (1/6 patients) d
 
G2 anorexia (1/6 patients) b
 
G2 increased total bilirubin (1/6 patients) b
 
G2 High TBL (1/6 patients) b
 
G3 DILI (1/6 patients) [DLT] c

a The DLT assessment period runs from the start of dosing with RXC004 (Cycle 0 Day 1) up to Cycle 1 Day 28. To be evaluable for DLT assessment patient must had received  $\geq$  66% of the intended dose of RXC004 and all of the nivolumab infusion during Cycle 1, or have experienced a DLT event in the assessment period.

b Related to RXC004.

c Related to RXC004 and nivolumab.

d Related to nivolumab.

e Two of the 8 patients who received RXC004 1.5 mg in combination with nivolumab discontinued prior to the end of Cycle 1 without meeting DLT criteria, and were replaced.

AE, adverse event; CTCAE, Common Terminology Criteria for Adverse Events; DLT, dose-limiting toxicity; q4w, every 4 weeks; QD, once daily.

A summary of the treatment-emergent adverse events (TEAEs) reported in Module 2 (RXC004 + nivolumab combination therapy) up to 01 July 2022 is presented in Table 9.

**Table 9      Summary of Treatment-Emergent Adverse Events as of 01 July 2022,  
Phase 1 study RXC004/0001 (RXC004 + Nivolumab Module 2)**

Number of patients with:	RXC004 1.0 mg + nivolumab (N=5)	RXC004 1.5 mg + nivolumab (N=8)	Overall (N=13)
TEAE	5 (100)	8 (100)	13 (100)
Treatment-Related TEAE	5 (100)	8 (100)	13 (100)
RXC004-Related TEAE	5 (100)	8 (100)	13 (100)
Nivolumab-Related TEAE	3 (60)	6 (75)	9 (69)
TEAE $\geq$ Grade 3	3 (60)	4 (50)	7 (54)
Treatment-Related TEAE $\geq$ Grade 3	1 (20)	3 (38)	4 (31)
RXC004-Related TEAE $\geq$ Grade 3	1 (20)	3 (38)	4 (31)
Nivolumab-Related TEAE $\geq$ Grade 3	0 (0)	2 (25)	2 (15)
TEAE $\geq$ Grade 4	0 (0)	0 (0)	0 (0)
Treatment-Related TEAE $\geq$ Grade 4	0 (0)	0 (0)	0 (0)
Serious TEAE	3 (60)	3 (38)	6 (46)
Serious Treatment-Related TEAE	0 (0)	1 (13)	1 (8)
Serious RXC004-Related TEAE	0 (0)	1 (13)	1 (8)
Serious nivolumab-Related TEAE	0 (0)	1 (13)	1 (8)
TEAE Leading to Discontinuation of Study Treatment (RXC004)	0 (0)	2 (25)	2 (15)
Treatment-Related TEAE Leading to Discontinuation of Study Treatment	0 (0)	2 (25)	2 (15)
TEAE Leading to RXC004 Dose Modification	2 (40)	5 (63)	7 (54)
Dose Reduced	0 (0)	1 (13)	1 (8)
Dose Interrupted	2 (40)	5 (63)	7 (54)
TEAE Leading to Death	0 (0)	0 (0)	0 (0)
TEAE of Dose Limiting Toxicity	0 (0)	1 (13)	1 (8)

Adverse events were coded using MedDRA Version 24.1. A TEAE was an AE with onset on or after date of first dose of study treatment and within 30 days of last dose.

Treatment-related adverse event was an adverse event that had relationship to study drug designated by the investigator as Possibly Related or Probably Related.

Treatment-Related: adverse events related to RXC004 and/or nivolumab. If the relationship to RXC004 or nivolumab was missing, the event was conservatively treated as related to the corresponding study treatment.

AE, adverse event; MedDRA, Medical Dictionary for Regulatory Activities; TEAE, treatment-emergent adverse event.

The most common TEAEs (that were reported by  $\geq$  20% of patients) are summarised by RXC004 dose level and overall in Table 10. The most common TEAEs were decreased appetite, fatigue, and nausea which were all reported for 6 patients each (46%).

**Table 10      Most common (occurring in at least 20% patients) TEAEs, as of 01 July 2022, Phase 1 study RXC004/0001 (RXC004 + nivolumab Module 2)**

Preferred term	Number (%) of patients		
	RXC004 1.0 mg QD + nivolumab (N = 5)	RXC004 1.5 mg QD + nivolumab (N = 8)	Overall (N = 13)
Patients with any TEAEs	5 (100)	8 (100)	13 (100)
Decreased appetite	2 (40)	4 (50)	6 (46)
Fatigue	3 (60)	3 (38)	6 (46)
Nausea	2 (40)	4 (50)	6 (46)
Dysgeusia	1 (20)	4 (50)	5 (38)
Constipation	2 (40)	2 (25)	4 (31)
Headache	2 (40)	2 (25)	4 (31)
Weight decreased	1 (20)	3 (38)	4 (31)
Abdominal distension	1 (20)	2 (25)	3 (23)
Blood bilirubin increased	0 (0)	3 (38)	3 (23)
Pruritus	1 (20)	2 (25)	3 (23)
Urinary tract infection	0 (0)	3 (38)	3 (23)

QD, once daily; TEAE, treatment-emergent adverse event.

#### 4.4.1.3 RXC004 pharmacokinetic profile

The data from the ongoing Phase 1 study (NCT03447470) have characterised the PK of RXC004 monotherapy in patients following single and multiple oral doses ranging from 0.5 mg to 10 mg, and in combination with standard dose nivolumab at doses of RXC004 1 mg and 1.5 mg.

RXC004 was rapidly absorbed following oral dosing in fasting conditions, with a peak plasma concentration observed typically after 1-2 hours post-dose and eliminated with a half-life of approximately **CCI** hours. The exposures achieved in patients dosed with 0.5–2 mg were broadly dose proportional and predictable from the exposure observed in the patient dosed at 10 mg in terms of half-life,  $C_{max}$ ,  $C_{min}$  and AUC. There was limited accumulation to steady state and it is in line with expectations from the measured half-life. The 3 mg dose  $C_{max}$ ,  $C_{min}$  and AUC were all disproportionately high compared to the 2 mg dose, giving an estimated **CCI** in exposure for the 50% rise in dose.

There was little difference in RXC004 plasma exposure between monotherapy and combination therapy on Cycle 0 Day 1. On Cycle 1 Day 15, the steady state RXC004 plasma exposure appeared to be slightly greater on combination therapy compared with monotherapy, although patient numbers are small. The mechanism for a potential small increase in exposure when RXC004 is given with nivolumab is unclear since a PK interaction with a monoclonal antibody is unlikely, but an increase in bioavailability cannot be ruled out.

The plasma exposure of RXC004 when given at 1.5 mg in combination with nivolumab was no greater than that observed at 2 mg monotherapy and was around **CCI** than that observed at 3 mg monotherapy.

The steady state PK parameters of RXC004 from Study RXC004/0001, for RXC004 monotherapy and in combination with nivolumab are summarised in Table 12.

**Table 12 Steady state pharmacokinetic parameters, as of 01 July 2022, Phase 1 study RXC004/0001 RXC004 monotherapy and combination with nivolumab (Module 1 and Module 2)**

Parameter (units)		RXC004 monotherapy			CCI	RXC004 in combination with nivolumab	
		1 mg	1.5 mg	2 mg		1 mg	1.5 mg
C min (ng/mL)	N	3	6	4	CCI	4	4
	Geometric mean (%CV)	7.15 (120)	12.6 (142)	26.8 (134)		8.62 (163)	13.6 (48.4)
T max (h)	N	3	6	5	CCI	5	6
	Median (min – max)	1.00 (1–2.00)	2.00 (1.00–4.00)	1.00 (0.5 – 2.00)		2.00 (0.5–6.0)	1.50 (0.5–2.00)
C max (ng/mL)	N	3	6	5	CCI	5	5
	Geometric mean (%CV)	42.4 (89.1)	56.6 (53.7)	68.5 (61.6)		58.2 (46.3)	76.4 (57.6)
AUC 0-24 (h*ng/mL)	N	3	6	4	CCI	5	5
	Geometric mean (%CV)	392 (42)	630 (76)	931 (61.1)		544 (65.5)	706 (40.1)

AUC0-24, area under the plasma concentration-time curve from zero to 24 hours; Cmax, maximum observed plasma concentration; Cmin, minimum observed plasma concentration across the dosing interval; Tmax, time to maximum plasma concentration.

#### **4.4.1.5 RXC004 monotherapy dose**

Based on all of the available information, patients who enrol in Arm A RXC004 monotherapy will receive 2.0 mg RXC004 orally once a day.

The 2 mg QD dose was both tolerable and able to consistently deliver Cmin values of **CCI** fold IC50 in all patients, whereas the 1.5 mg QD dose did not consistently achieve the target Cmin values of **CCI** fold IC50 in all patients.

The 2 mg dose has been selected for Phase 2 development as the optimal dose to demonstrate an efficacy signal in patients with genetically selected tumours and to allow for potential dose reductions to manage adverse events.

#### **4.4.1.6 RXC004 dose in combination with nivolumab**

Patients who receive combination therapy with RXC004 and nivolumab in Arm A or B will receive RXC004 1.5 mg orally once a day. Justification for the choice of doses and regimens is provided in Sections 4.4.1 and 4.4.2.

#### **4.4.2 Nivolumab**

The nivolumab dose and regimen selected for this study are based on the FDA approved prescribing information for nivolumab. Patients with MSI-H or dMMR metastatic colorectal cancer can receive 240 mg q2w or 480 mg q4w. 480 mg q4w was selected to complement a 28-day cycle of RXC004 and reduce the number of patient visits required.

### **4.5 End of Study Definition**

A participant is considered to have completed the study if he/she has completed all phases of the study (including the last visit and the last scheduled assessment shown in the Schedule of Assessments) or withdraws consent whichever occurs first.

The end of the study is defined as the date of the last visit of the last participant in the study or the last scheduled assessment shown in the Schedule of Assessments for the last participant in the study before the data cut off (DCO).

Sponsor may terminate this study at any time for reasons that include but are not limited to;

- The discovery of an unexpected, significant, or unacceptable risk to the patients enrolled in the study
- Inability to complete the trial in a meaningful timeframe due to a lack of recruitment.
- A decision on the part of the Sponsor to modify/suspend or discontinue development of the drug

## 5 STUDY POPULATION

The study will recruit male or female patients aged 18 years or older with histologically documented, RNF43 or RSPO genetically aberrated, MSS mCRC (Stage IV), who have progressed after standard of care treatment(s), have a minimum life expectancy of 16 weeks and an Eastern Cooperative Oncology Group performance status of 0 or 1.

Prospective approval of protocol deviations to recruitment and enrolment criteria, also known as protocol waivers or exemptions, is not permitted.

### 5.1 Inclusion Criteria

Participants are eligible to be included in the study only if all of the following criteria apply:

- 1 Participant must be  $\geq 18$  years of age at the time of signing the informed consent.
- 2 Ability to give written informed consent and capable of understanding the protocol requirements listed in the informed consent form (ICF). Written informed consent must be obtained prior to performing any protocol-related procedures, including screening and pre-screening evaluations. Participants must be willing and able to comply with the study protocol procedures and restrictions.
- 3 Histological documentation of metastatic (Stage IV) CRC and;
  - (a) documented tumour tissue aberration in RNF43 and/or RSPO from central pre-screening or from a recognised panel approved by the sponsor. Please see Section 5.5 and Appendix F for more details
  - (b) documented confirmation of MSS status, performed as a standard of care procedure at site. Please see Section 5.5 for more details
- 4 Patients must have had documented radiological progression following a minimum of 1 prior standard of care treatment regimen for metastatic disease.
- 5 ECOG performance status 0 or 1 with no deterioration over the previous 2 weeks and an estimated life expectancy of greater than 16 weeks
- 6 At least one lesion that is measurable by RECIST 1.1 at baseline (within 28 days prior to start of study treatment). The measurable lesion must not be chosen for the mandatory paired biopsies.
- 7 Mandatory paired biopsies\*; Patients must have at least one lesion suitable for biopsy at screening (which must not be a target lesion for RECIST 1.1) and be willing to provide mandatory tumour biopsy samples as follows:

**Arm A:** Baseline\*; C1D15 (+ up to 7 days) and during Cycle 3 of monotherapy treatment (3 biopsies)

**Arm A combination treatment phase patients:** Baseline\*, C1D15 (+ up to 7 days) and during Cycle 3 of combination treatment (3 biopsies)

**Arm B:** Baseline\*\*, C1D15 (+ up to 7 days) and during Cycle 3 of combination treatment (3 biopsies)

\*Baseline biopsy is mandatory except in exceptional circumstances where biopsy is not technically feasible. All patients without a baseline sample must be approved by Sponsor before starting study treatment. On treatment biopsies are also mandatory unless deemed not to be technically or clinically feasible by Investigator.

\*\*~~CCI~~ [REDACTED], ideally from the same site of disease (e.g. liver, lymph node etc) that the 'on treatment' biopsy will be taken from, and taken after completion of all prior standard of care treatments will be accepted as a baseline biopsy.

- 8 Patients with adequate organ functions as described below;
  - AST/ALT  $\leq$  2.5X ULN (upper limit of normal) [with no underlying Liver Metastasis]
  - AST/ALT  $\leq$  5 X ULN [with underlying Liver Metastasis]
  - Total Bilirubin  $\leq$  1.5 X ULN
  - Serum Creatinine  $\leq$  1.5 X ULN
  - ANC  $\geq$  1.5  $\times$  10^9/L
  - Platelets  $>$  100  $\times$  10^9/L
  - Hb  $>$  8.5g/dL (with or without transfusional support)
  - Calculated creatinine clearance (CrCL)  $\geq$  60 mL/min as determined by Cockcroft Gault (using actual body weight).

Males:

$$\text{CrCL} = \frac{\text{Weight (kg)} \times (140 - \text{Age})}{72 \times \text{serum creatinine (mg/dL)}}$$

Females:

$$\text{CrCL} = \frac{\text{Weight (kg)} \times (140 - \text{Age})}{72 \times \text{serum creatinine (mg/dL)}} \times 0.85$$

- 9 Female patients of childbearing potential must have a negative pregnancy test prior to start of dosing
- 10 Female patients of childbearing potential and male patients with female partners of childbearing potential must agree to use a highly effective method of contraception during the study and for at least 5 months after the last dose of study drug. See Section 5.3.1 for details of acceptable methods of contraception

**For patients on RXC004 monotherapy treatment (Arm A) the following inclusion criteria will also apply to enter the RXC004 + nivolumab treatment phase;**

11. Patients must have had documented RECIST1.1 defined radiological progression on RXC004 monotherapy treatment on the first scheduled scan (week 8 +/- 1 week)
12. Patients must receive Cycle 1 Day 1 of combination study treatment within 28 days of the first scheduled scan (week 8 +/- 1 week) showing RECIST1.1 defined radiological progression, or for clinically stable patients that remain on RXC004 after RECIST1.1 defined radiological progression, within 28 days of the most recent scan showing further radiological progression or confirmation of the week 8 RECIST1.1 progression (see Section 7.1.1 and Appendix D for more details)

## 5.2 Exclusion Criteria

Participants are excluded from the study if any of the following criteria apply:

- 1 Prior therapy with a compound of the same mechanism of action as RXC004.
- 2 Patients at higher risk of bone fractures, including:
  - (a) Patients with Vitamin D [25(OH)D3] deficiency defined as < 30 nmol/L (<12 ng/mL). [Note - Patients who fail on this criteria can be retested within the screening window]
  - (b) Patients with a corrected total serum calcium level of <2 mmol/L and serum magnesium level of < 0.60 mmol/L
  - (c) Patients with osteoporosis (as defined by a T-score of < -2.5 at any of the 3 following sites, all of which must be assessed: L/R total hip, L/R femoral neck, lumbar spine (L1-4) by DEXA scan) or history of fragility fractures (any fracture occurring with low-level trauma or as a result of falling < standing height)
  - (d) Patients with ongoing or a history of clinically significant hyperparathyroidism, Pagets disease or Osteomalacia. Patients with a prior diagnosis of hyperparathyroidism, Pagets disease or Osteomalacia, considered to have no increased bone fragility risk, may be included only after consultation with the Sponsor's Medical Monitor.
  - (e) Patients who have received treatment for type 2 Diabetes Mellitus with a Thiazolidinedione peroxisome proliferator-activated receptor gamma agonist (e.g. pioglitazone or rosiglitazone) within 4 weeks prior to study drug dosing.
- 3 Any known uncontrolled inter-current illness or persistent clinically significant toxicity related to prior anti-cancer treatment (as assessed by the Investigator) which in the investigator's opinion makes it undesirable for the patient to participate in the study
- 4 Patients who have any history of an active (requiring treatment) other malignancy (except any in-situ carcinoma, non-melanoma skin carcinoma and early prostate cancer with a normal PSA) within 2 years of study entry.
- 5 Patients with known or suspected brain metastases

- 6 Use of anti-neoplastic agents (including immunotherapy), immunosuppressants and other investigational drugs within 3 weeks prior to the first dose of study treatment, or any residual AEs from prior anti-cancer therapies that have not resolved to Grade  $\leq 1$ . Note: COVID-19 vaccinations that are authorised but not approved should not be considered as investigational agents for the purposes of study eligibility assessment.
- 7 Patients with a known hypersensitivity to any RXC004 excipients.
- 8 Patients with a contra-indication for denosumab treatment including:
  - Known hypersensitivity to Denosumab or any of the excipients
  - Severe untreated hypocalcaemia
  - Unhealed lesions from dental or oral surgery
- 9 Patients who are pregnant or breast-feeding
- 10 Use of any live or live-attenuated vaccines against infectious diseases (e.g., influenza nasal spray, varicella) within 4 weeks (28 days) of initiation of study treatment. Note: Patients who require COVID-19 vaccination within 4 weeks of initiation of study treatment should receive a non-live vaccine (e.g. one based on mRNA or fully inactivated/genetically modified viruses incapable of replication)
- 11 Judgment by the investigator that the participant should not participate in the study if the participant is unlikely to comply with study procedures, restrictions and requirements.
- 12 Patients with a mean resting corrected QTcF  $>470$  ms, obtained from triplicate ECGs performed at screening

**For patients on RXC004 + nivolumab combination treatment (Arm B or Arm A RXC004 + nivolumab treatment phase) the following exclusion criteria will also apply;**

- 13 Patients with any contraindication to the use of nivolumab as per approved label (Summary of Product Characteristics or equivalent)
- 14 Patients with active or prior documented autoimmune or inflammatory disorders within the past 5 years, including inflammatory bowel disease, rheumatoid arthritis, autoimmune hepatitis, Grave's disease, lupus and celiac disease. The following are exceptions to this criterion;
  - (a) Patients with vitiligo or alopecia
  - (b) Patients with type I diabetes mellitus
  - (c) Patients with residual hypothyroidism due to autoimmune condition only requiring hormone replacement
  - (d) Patients with psoriasis not requiring systemic treatment, or conditions not expected to recur in the absence of an external trigger.
  - (e) Patients with celiac disease controlled by diet alone
- 15 Patients with active infections, including tuberculosis, hepatitis B, hepatitis C or human immunodeficiency virus. Patients with a resolved HBV infection (defined as presence of

hepatitis B core antibody [HBcAb] and absence of HBV surface antigen [HBsAg] or negative on polymerase chain reaction [PCR] for HBV DNA) are eligible. Patients positive for HCV antibody are eligible only if PCR is negative for HCV RNA.

- 16 Patients with body weight <40kg
- 17 Patients with a history of allogeneic organ transplant or active primary immunodeficiency
- 18 Patients with a known hypersensitivity to nivolumab or any of the excipients of the product

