### **Bone Events**

Since Wnt inhibition both reduces bone formation and increases bone resorption, the concomitant use of the anti-resorbing agent, denosumab is expected to prevent drug-induced bone loss, and this has been a successful approach in the Phase 1 study, along with patient selection, and monitoring. Patients with high risk of bone fractures are excluded study protocols and participating patients will be monitored for bone turnover biomarkers and bone mineral density while on study.

In this study, patients will receive prophylactic denosumab (120 mg s.c. once every month) along with Vitamin D3 and Calcium supplements (800 IU vitamin D3 daily [Cholecalciferol] and 1000-1500 mg calcium daily supplements) from the time of signing the ICF and throughout the study until discontinuation of RXC004.

Guidance for dose modifications of RXC004 and nivolumab for all toxicities are provided in Section 6.6. Bone toxicity events are defined as an AEPI for RXC004, requiring additional details to be recorded on routine safety reporting.

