## 5.4 Screen Failures

Screen failures are defined as participants who consent to participate in the clinical study but are not subsequently treated in the study. A minimal set of screen failure information is required to ensure transparent reporting of screen failure participants to meet the Consolidated Standards of Reporting Trials (CONSORT) publishing requirements and to respond to queries from regulatory authorities. Minimal information includes demography, screen failure details, eligibility criteria, and any serious adverse event (SAE).

Individuals who do not meet the Calcium and/or Vitamin D3 laboratory criteria for participation in this study may be retested after starting Calcium/Vitamin D3 supplementation. Repeating laboratory tests within the screening period will not be considered as a rescreen.

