## **8.2      Safety Assessments**

### **8.2.1      Clinical Safety Laboratory Assessments**

Blood samples for determination of clinical chemistry and haematology will be taken at the visits indicated in the SoA. Additional safety samples may be collected if clinically indicated at the discretion of the investigator. The date, time of collection and results (values, units and reference ranges) will be recorded on the appropriate eCRF.

The clinical chemistry and haematology will be performed at a local laboratory at or near to the investigator site. Sample tubes and sample sizes may vary depending on laboratory method used and routine practice at the site.

The following laboratory variables will be measured.

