**Table 16      Laboratory safety variables**

Haematology/Haemostasis (whole blood)	Clinical Chemistry (serum or plasma)
Haemoglobin (Hb)	Creatinine and creatinine clearance a
Total white cell count	Bilirubin, total
Neutrophils (absolute count or %)	Alkaline phosphatise (ALP)
Platelet count	Aspartate transaminase (AST)
Lymphocytes (absolute count or %)	Alanine transaminase (ALT)
	Albumin
	Potassium
Other tests:	Calcium, total
HIV antibodies c	Phosphate
Hepatitis B surface antigen c	Sodium
Hepatitis C antibodies c	Glucose
	Thyroid-stimulating hormone (TSH)
	Lipase
	Lactate dehydrogenase (LDH)
	Amylase
	T3 free (reflex) b
	T4 free (reflex) b
	C-reactive protein (CRP)
	Vitamin D c

a Creatinine clearance at baseline only

b Free T3 or T4 only need to be measured if TSH is abnormal or if Investigator judges that there may be an AE related to the endocrine system

c Required at baseline/screening only.

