4.12.3 Clinical Laboratory Evaluation

Blood samples for determination of clinical chemistry and haematology will be taken at the visits indicated in the SoA (see protocol). Additional safety samples may be collected if clinically indicated at the discretion of the investigator. The date, time of collection and results (values, units and reference ranges) will be recorded on the eCRF.

The clinical chemistry and haematology will be performed at a local laboratory at or near to the investigator site. Sample tubes and sample sizes may vary depending on laboratory method used and routine practice at the site.

In case of BLQ values (eg “<5”, “<100”) for some assessments, the following rule will be considered:

- If less than 50% of the assessments (across patients) are BLQ such as “<XXX”, then “XXX/2” will be considered for summaries.

- If 50% or more than 50% of assessments (across patients) are BLQ such as “<XXX” then “0” will be considered for summaries.

The following laboratory variables will be measured:

- Haematology (whole blood): Haemoglobin (Hb), Lymphocytes (absolute count and %), Neutrophils (absolute count and %), Platelet count, Total white cell count. . .
- Clinical Chemistry (serum or plasma): Albumin, Alanine transaminase (ALT), Alkaline phosphatase (ALP), Amylase (only for arm B), Aspartate transaminase (AST), Calcium, Calcium corrected, Creatinine, CRP, Glucose, Lactate dehydrogenase (LDH), Lipase (only for arm B), Magnesium, Phosphate, Potassium, Sodium, Total bilirubin, Urea. . .

The original lab test units will be converted using the International System of Units (SI) [11].

Laboratory test with numerical grading criteria in the NCI CTCAE v5.0 will be graded accordingly. Grade 0 will be assigned for all non-missing values not graded as 1 or higher. For laboratory tests where grades are not defined by CTCAE v5.0 results will be classified as low, normal or high based on laboratory normal ranges.

The following summaries will be provided for all parameters for arm A and arm B:

- A summary of results by assessment visit (as per SoA)
- Shift tables will be provided for all parameters to compare a patient’s baseline laboratory grade relative to worst post-baseline grade (Low and/or High abnormal direction will be considered for each parameter).

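### Exclusion 2(b) is ambiguous: read literally it does not exclude isolated corrected calcium <2 mmol/L before mandatory denosumab

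*Protocol*

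**What the plan says.** Protocol Section 5.2 excludes a patient who meets any one listed criterion. Exclusion 2 covers raised fracture risk through an open list. Item (b) of that list is a "corrected total serum calcium level of <2 mmol/L and serum magnesium level of < 0.60 mmol/L". Neighbouring items join alternatives with *or*: 2(c) runs "by DEXA scan) or history of fragility fractures", and 2(d) covers "Patients with ongoing or a history of clinically significant hyperparathyroidism, Pagets disease or Osteomalacia".

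Section 5.4 adds a retest rule: "Individuals who do not meet the Calcium and/or Vitamin D3 laboratory criteria for participation in this study may be retested" once supplementation has started. It does not mention magnesium.

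Exclusion 8 lists contraindications to denosumab, again as an open list. Its only calcium entry is hypocalcaemia that is both severe and untreated, with no numeric limit. The footnotes to Tables 1 and 2 require denosumab before the first RXC004 dose in both arms. Calcium and vitamin D3 supplements begin when the consent form is signed.

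On measurement, Section 8.2.1 introduces Table 16 with "The following laboratory variables will be measured". The table lists total calcium and albumin but not magnesium, although it has a footnote for tests "Required at baseline/screening only". SAP Section 4.12.3 does list magnesium: "Lipase (only for arm B), Magnesium, Phosphate, Potassium, Sodium, Total bilirubin, Urea".

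**The concern.** The Bone Events text in Section 2.3.1.2 relies on selection as one protection: "Patients with high risk of bone fractures are excluded study protocols". Exclusion 2(b) is the part of that selection that puts a number on calcium. It sits ahead of denosumab, which Section 6.2.3 says is used here outside its label and which is given to everyone.

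If a site applies 2(b) as a joint condition, low calcium with normal magnesium passes the numeric screen. Exclusion 8 is a weak substitute. It has no threshold, it requires severity, and a patient who began calcium supplements at consent can be argued to be already treated.

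Two sites could therefore decide differently on the same patient. Sections 5 and 8 do not allow waivers, and SAP Section 4.4.2 requires eligibility violations to be graded minor or major. Both presuppose that it is clear who meets 2(b).

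**Working it through.** The plan states no figure on this point, so the check is one of logic and of comparing texts.

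**1. What each reading excludes.** The inputs are the two limits in 2(b): corrected calcium (Ca) <2 mmol/L and magnesium (Mg) <0.60 mmol/L.

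| Ca (mmol/L) | Mg (mmol/L) | Both must be low (literal) | Ca alone | Either low (*or*) |
|---|---|---|---|---|
| <2 | <0.60 | excluded | excluded | excluded |
| <2 | ≥0.60 | **not excluded** | excluded | excluded |
| ≥2 | <0.60 | not excluded | not excluded | excluded |
| ≥2 | ≥0.60 | not excluded | not excluded | not excluded |

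The literal rule and a calcium-alone rule differ in the second row only. Changing the connector to *or* also moves the third row. Once low calcium excludes on its own, a joint calcium-and-magnesium condition adds nobody, because the first row is already covered.

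**2. Does the lead-in settle it?** No. The rule that any one criterion is enough works between criteria. It does not change a connector inside 2(b).

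**3. Does the usage of *and* in Section 5.2 settle it?** No. Items 2(c) and 2(d) use *or* for alternatives, which favours reading *and* as joint. Exclusion 6 points the other way: it joins anti-neoplastic agents, immunosuppressants and other investigational drugs with *and*, and any one class within 3 weeks is plainly meant to exclude.

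**4. Does Section 5.4 settle it?** Not fully. It treats calcium as something a patient can fail, and it separates calcium from vitamin D3. It does not separate calcium from magnesium. A patient who failed a joint 2(b) could also be retested after calcium supplements, so the section fits both readings.

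**5. Is the magnesium value available?** SAP Section 4.12.3 names 18 chemistry variables. Table 16 lists 15 of them. One more, corrected calcium, can be derived from total calcium and albumin. Two are absent, magnesium and urea: 15 + 1 + 2 = 18. Of those two, only magnesium carries an eligibility limit.

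**The case against.** The strongest reply is that sites would read 2(b) sensibly. *And* joins alternatives in exclusion 6, Section 5.4 speaks of calcium criteria, and the list in exclusion 2 is open. Several other safeguards also apply:

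- the open list in exclusion 8;
- the judgement in exclusion 3 on uncontrolled illness;
- calcium and vitamin D3 from consent;
- chemistry at screening and on Cycle 0 Day 1;
- the individual benefit-risk assessment required before denosumab (Table 1 footnote w, Table 2 footnote s).

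Most of this stands, and it is why the point is minor. The benefit-risk assessment counts as a partial safeguard only, because it appears in a footnote on dental examination. The rest either depends on judgement or lowers the risk without setting a limit. A numeric criterion exists so that judgement is not the only barrier, and the connector weakens that.

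Three stronger readings are tempting, and the documents do not support them:

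- *Section 5.4 contradicts 2(b).* It is compatible with a joint rule (step 4), so it is a hint about intent and not a conflict.
- *Magnesium is not collected.* Criterion 2(b) itself requires the value, Section 8 requires screening evaluations to be completed so that all criteria can be confirmed, and the SAP lists magnesium. The missing Table 16 line is a consistency matter.
- *Low magnesium alone was meant to exclude.* No text says so.

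**Conclusion.** The point holds as an ambiguity in an operative safety rule. On the literal reading, one patient type is not caught by 2(b): corrected calcium <2 mmol/L with magnesium ≥0.60 mmol/L. On the either-value reading there is no gap, and the documents do not say which was intended. The number of patients affected cannot be derived from the documents.

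The case for change rests on three facts. Denosumab is mandatory in both arms, 2(b) is the only numeric calcium limit in the eligibility criteria, and exclusion 8 supplies no threshold. It does not assume that any patient has been wrongly enrolled or harmed, and nothing in the documents shows that. Endpoints and sample size are unaffected. Only the calcium wording carries the recommendation; the magnesium items are a question to the sponsor and a table edit.

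**What to change.** Reword 2(b) so that corrected total serum calcium <2 mmol/L excludes on its own, and keep the existing Section 5.4 retest after supplementation.

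Ask the sponsor to decide on magnesium:

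- If magnesium <0.60 mmol/L should also exclude on its own, join the two limits with *or*, add magnesium to Table 16 as a screening test, and consider extending the Section 5.4 retest to it.
- If not, drop magnesium from 2(b), since a joint condition would add nobody once calcium stands alone.

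The text change is small, but altering an exclusion criterion is a protocol amendment, and Appendix A 1 requires ethics committee and applicable regulatory approval before it takes effect. The other cost is possibly a few more screen failures or retests, in a population already narrowed to RNF43 loss-of-function mutations (3-13% of colorectal cancers, Section 2.2.1) or RSPO rearrangements (about 5%). Combining this with the next planned amendment would keep the cost low.
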